7.2.3.1 Sensitivity analysis

Sensitivity analyses include refitting the MMRM model used for the secondary analysis using the following data instead of the data defined in Section 7.2.1:

1. UACR obtained from the first morning void samples (baseline, day 1, 8, 15, 30, 60, 90).
2. In case a considerable number of cases with the protocol deviation “Spot urine collected not being First Morning Void” (PD code “Oth03”) are identified, a sensitivity analysis of UPCR and UACR from FMV excluding these will be considered.

8 Statistical methods for safety and tolerability data

Analyses of all safety data (Adverse events, vital signs, ECG intervals, laboratory measurements) produced at IA2 will be rerun after DBL as a part of the final analysis in order to account for data changes between IA2 and DBL in ongoing adverse events, laboratory abnormalities and safety laboratory evaluations.

8.1 Variables

Adverse events, vital signs (blood pressure, pulse rate, body temperature), ECG intervals, laboratory measurements, as well as subject demographics, baseline characteristics, and treatment information.

Baseline for all variables, is defined to be the last measurement prior to the start of study drug administration.

8.2 Descriptive analyses

All subjects within the SAF (up to Day 90), SAF1 and SAF2 will be included in the safety data analysis separately, except background and demographic characteristics which will be included in the FAS data analysis.

Subject demographics

All data for demographic variables will be listed by treatment group and subject. Summary statistics will be provided by treatment group overall.

Relevant medical history, current medical conditions, results of laboratory screens, drug tests and any other relevant information will be listed by treatment group and subject, overall and for each study part separately.

The FAS will be used for these analyses.

Baseline characteristics

All data for background variables will be listed by treatment group and subject. Baseline characteristics include but are not limited to UPCR, eGFR, and Renal biopsy information (Oxford Classification). Summary statistics will be provided by treatment group overall.

Renal biopsies used to assess study inclusion will be scored according to the Oxford classification and will be summarized descriptively by providing the frequency (n, %) of patients in the following categories:

- Mesangial score: ≤ 0.5 (M0) or >0.5 (M1)
- Endocapillary hypercellularity: absent (E0) or present (E1)

- Segmental glomerulosclerosis: absent (S0) or present (S1)
- Tubular atrophy/interstitial fibrosis: $\leq 25\%$ (T0), 26–50% (T1), or $> 50\%$ (T2)
- Cellular / fibrocellular crescents: none (C0), at least 1 (C1), in at least 25% of glomeruli (C2)

The total number of glomeruli will be also summarized separately.

UPCR and eGFR will be analyzed as continuous variables. In addition, the frequency (n, %) of patients with UPCR $< 200\text{mg}/\text{mmol}$ and $\geq 200\text{ mg}/\text{mmol}$, and eGFR $< 60\text{ mL}/\text{min}/1.73\text{m}^2$ and $\geq 60\text{ mL}/\text{min}/1.73\text{m}^2$ will be provided.

The FAS will be used for these analyses.

Treatment

Treatment exposure (days) will be summarized as a continuous variable by descriptive statistics. The duration of treatment exposure (in days) is defined as the last known date the patient took the study drug – the first day the patient took the study drug + 1, regardless of any temporary treatment interruption. Treatment exposure and reasons for discontinuation of study drug will be summarized by treatment group, for the SAF (up to Day 90) and for SAF1 and SAF2 separately.

Data for study drug administration, corticosteroid or immunosuppressant therapy (CS/IS) (as shown in Section 13) and concomitant medication and non-drug therapies will be listed by treatment group and subject.

Concomitant medications prior to randomization will be summarized by therapeutic class, PT and treatment group for the SAF. Concomitant medications after randomization will be likewise summarized for the SAF (to Day 90), SAF1 and SAF2 separately. Use of corticosteroid or immunosuppressant therapy (CS/IS) will be summarized. Significant non-drug therapies/procedures will also be summarized by ATC class and concomitant medication category and treatment group.

A summary of compliance of vaccination by vaccine type and treatment, will be tabulated.

Vital signs

All vital signs data will be listed by treatment, subject, and visit/time and if ranges are available, abnormalities (and relevant orthostatic changes) will be flagged.

Vital signs should be within the following ranges:

- Body temperature between 35.0-37.5°C
- Systolic blood pressure between 90-160 mm Hg
- Diastolic blood pressure, 50-90 mm Hg
- Pulse rate, 40-90bpm

Summary statistics will be provided by treatment and visit/time for the SAF (up to Day 90) and for SAF1 and SAF2 separately. Summary statistics will include mean, SD, CV, Q1, median, Q3, minimum and maximum as appropriate.

To assess the effect of LNP023 on blood pressure after dosing with LNP023, blood pressure and heart rate at 1 and 2 hours post dose on Day 1, and 2 hours post dose on Day 30 expressed as change from baseline will be graphically presented by treatment, for the SAF. This represents the blood pressure at the approximate time of C_{max} after first dose and at steady state. The relationship between changes in blood pressure and heart rate, and the C_{max} concentrations will also be investigated graphically.

ECG evaluations

All ECG data (including but not limited to QTcF prolongation, QT interval and HR) will be listed by treatment, subject and visit/time and abnormalities will be flagged.

Summary statistics will be provided by treatment and visit/timepoint, for the SAF (up to Day 90) and for SAF1 and SAF2 separately, and the frequency of (n, %) patients with the following abnormalities will be displayed:

- QRS > 120 ms
- QRS increase from baseline > 25%
- QTcF > 500ms
- QTcF increase from baseline > 60 ms
- Resting heart rate sinus rhythm (HR) < 30 bpm
- HR decrease from baseline \geq 25%
- HR > 130 bpm

Clinical laboratory evaluations

All laboratory data will be listed by treatment, subject, and visit/time and if normal ranges are available abnormalities will be flagged. A separate listing will be provided presenting all parameters in a subject with any abnormal values. Summary statistics will be provided by treatment and visit/time, for the SAF (up to Day 90) and for SAF1 and SAF2 separately. Summary statistics will include mean, SD, CV, Q1, median, Q3, minimum and maximum as appropriate. Values less than the Lower Limit (LL) will be imputed as $0.5 \times LL$ and values greater than the Upper Limit (UL) will be imputed as $1.5 \times UL$. The number and percentage of values below the LL and above the UL will be presented. For the figures, imputed values will be displayed.

Adverse events

All information obtained on adverse events will be displayed by treatment and subject. All information obtained on deaths will be likewise provided.

The overall incidence of treatment emergent AEs will be summarized by treatment group for the SAF (up to Day 90), SAF, SAF1 and SAF2 populations separately.

The number and percentage of subjects with adverse events will be tabulated by body system organ class (SOC) and preferred term (PT) with a breakdown by treatment, for the SAF (up to Day 90) and for SAF1 and SAF2 separately. A subject with multiple adverse events within a

body system is only counted once towards the total of this body system and treatment, for the event with highest severity. Summaries of SAEs will be provided in a similar manner.

A summary table of AEs leading to discontinuation of study treatment by preferred term will be produced for the SAF (up to Day 90), SAF1 and SAF2 separately.

Exposure-adjusted AE summaries will also be likewise considered for SAF.

For summary tables on exposure-adjusted AEs, the number of episodes per 100 patient months will be presented. The occurrence rate (number of episodes per 100 patient month) will be calculated as $100 \times (\text{the total number of AE episodes from all patients in the population divided by the total number of patient-months})$. A patient may have multiple occurrences of the same event. All occurrences are counted. Total patient months will be computed as $(\text{sum of the duration of exposure over patients, in days})/30.4375$. This method will account for the length of follow-up time under the assumption that events would occur with the same frequency at any point in time.

In addition, 95% confidence intervals will be presented for the occurrence rate. It will be assumed that for each of n subjects the time t_j ($j=1, \dots, n$) represents the duration of exposure to study treatment. The sequence of occurrences of an event will be modeled to follow approximately a Poisson process with constant intensity θ . The rate parameter θ will be estimated as $\lambda = D/T$, where $T = \sum_{j=1}^n t_j$ and D is the total number of events. Conditionally on T , an exact $100 \times (1-\alpha)\%$ confidence interval for a Poisson variable with parameter θT and observed value D can be obtained based on (Garwood, 1936), from which an exact $100 \times (1-\alpha)\%$ confidence interval for $100 \times D/T$ will be derived as follows (Sahai, 1993):

Lower confidence limit $L = \frac{0.5c_{\alpha/2, 2D}}{T} * 100$ for $D > 0$, 0 otherwise,

Upper confidence limit $U = \frac{0.5c_{1-\alpha/2, 2D+2}}{T} * 100$ for $D > 0$, 0 otherwise,

where $c_{\alpha, k}$ is the α th quantile of the Chi-square distribution with k degrees of freedom.

Adverse events of special interest definitions are found in the compound electronic Case Retrieval Strategy (eCRS). The classification reflects the current version of the Development Safety Profiling Plan (DSPP) and might be updated based on review of accumulating data. A listing of the case retrieval strategy will be presented.

The frequency and percentage of patients with adverse events of special interest will be presented by MedDRA preferred term and treatment arm. These outputs will also be produced for the SAF (up to Day 90) and for SAF1 and SAF2 separately.

Further displays of AEs may be produced in order to appropriately describe the outcomes seen in this trial. For displays of Treatment Emergent events only, events will be considered as Treatment emergent if they started after the date of first administration of study treatment (or were present prior to start of study treatment but increased in severity based on preferred term) and up to 7 days after study treatment discontinuation. For post-treatment period, AEs and SAEs will be summarized separately for both SAF1 and SAF2 analysis sets.

For TEAE tables on SAF (Part 1 and Part 2 to Day 90) a cut-off of 90 + 7 days (post end of treatment) for Part 1 patients and Part 2 patients on 90 days of treatment will be used, whereas a cut-off of 90 days for Part 2 patients on 180 days of treatment will be used.

For the legal requirements of ClinicalTrials.gov and EudraCT, two required Safety disclosure tables on treatment emergent adverse events which are not serious adverse events with an incidence greater than a certain threshold based on the final database and on treatment emergent serious adverse events and SAE suspected to be related to study treatment will be provided by system organ class and preferred term on the safety set population.

If for a same patient, several consecutive AEs (irrespective of study treatment causality, seriousness and severity) occurred with the same SOC and PT:

- a single occurrence will be counted if there is ≤ 1 day gap between the end date of the preceding AE and the start date of the consecutive AE
- more than one occurrence will be counted if there is > 1 day gap between the end date of the preceding AE and the start date of the consecutive AE.

For occurrence, the presence of at least one SAE / SAE suspected to be related to study treatment / non SAE has to be checked in a block e.g., among AE's in a ≤ 1 day gap block, if at least one SAE is occurring, then one occurrence is calculated for that SAE.

The number of deaths resulting from SAEs suspected to be related to study treatment and SAEs irrespective of study treatment relationship will be provided by SOC and PT.

Physical Examination

Significant findings prior to informed consent will be recorded in the Medical history eCRF and any significant findings after informed consent will be recorded on the Adverse Events and thus will be summarized respectively.

Protocol deviations

Protocol deviations will be listed by treatment, subject and epoch period. A frequency summary table will be produced by treatment period for all protocol deviations (including Covid related).

Others

All pregnancy data will be listed by treatment, subject, and visit/time.

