3.6.2.5 Non-clinical safety findings of undetermined relevance

In toxicology studies with LNP023, a few findings were observed that are considered of undetermined relevance based on current knowledge. These have not been seen in the clinical setting thus far, and there is no evidence to conclude that these have a causal association with LNP023 exposure or an impact on the risk-benefit balance of LNP023.

Cardiovascular effects: LNP023 in medium to high doses in dogs elicited peripheral vasodilatation, reducing the total peripheral resistance and blood pressure in addition to causing compensatory heart rate increase. At the highest doses, pathological changes were noted in the dogs. The response may be present in humans, even though it was not seen in other species. Small QTc effects were observed at high doses and exposures in nonhuman primates, but in no other species. The risk for humans is considered to be small, but vital signs, ECGs and cardiac AEs will be closely monitored. See [Section 8.6.7](#)

Hyperbilirubinemia: In the 4-week GLP toxicological study, a significant dose-dependent effect was observed on the conjugated bilirubin levels in rats and dogs. The effect was considered to be minimal to mild. No change was observed in liver enzymes and the effect was reversible in all animals. Increased bilirubin was accompanied by bile duct hyperplasia in one high-dose dog. At this point it is not known if the hyperbilirubinemia is translatable to humans. Liver function tests and hepatic AEs will be closely monitored in the LNP023 program. See [Section 8.6.8](#).

Proteinuria: This finding was observed in rats treated with high doses of LNP023 (1,000 mg/kg), but electron microscopy did not reveal any morphological changes. The effect was fully reversible, and morphological changes and proteinuria were not observed in dogs. Urine and renal function will be closely monitored. See [Section 8.8.4](#)

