8.6.7 Electrocardiogram (ECG)

Full details of all procedures relating to the ECG collection and reporting are contained in the Site Operations Manual.

All ECGs are done as 12-lead triplicate ECGs. All ECGs evaluations will be done by the investigators.

PR interval, QRS duration, heart rate, RR interval, QT interval, QTc.

The Fridericia QT correction formula (QTcF) must be used for clinical decisions.

As applicable, QTcF and QTcB may be calculated in-house. Unless auto-calculated by the ECG machine, the investigator must calculate QTcF at the Screening and/or Baseline visit(s) (as applicable) to assess patient eligibility. See the Site Operations Manual for additional details.

Clinically significant abnormalities must be reported in the AE CRF.

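### The ECG abnormality table counts relative heart-rate falls but has no matching row for rises, although the one heart-rate signal named in the protocol is a rise

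*SAP*

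**What the plan says.** The ECG part of SAP section 8.2 sets out seven abnormalities to be shown as the number and percentage of patients, by treatment and visit. Three concern heart rate:

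- a low absolute value, "Resting heart rate sinus rhythm (HR) < 30 bpm";
- a relative fall, "HR decrease from baseline" of at least 25%;
- a high absolute value, above 130 bpm.

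No row counts a relative rise in heart rate. The other intervals are checked upwards: QRS has an absolute row and a relative-increase row, and QTcF has an absolute row and "QTcF increase from baseline > 60 ms".

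Protocol section 3.6.2.5 describes the cardiovascular findings behind this monitoring. At medium to high doses in dogs, the drug caused peripheral vasodilatation, "reducing the total peripheral resistance and blood pressure in addition to causing compensatory heart rate increase". The section adds that the response could be present in humans although other species did not show it. It also reports that "Small QTc effects were observed at high doses and exposures in nonhuman primates", and it undertakes that "vital signs, ECGs and cardiac AEs will be closely monitored".

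ECG abnormality counts by treatment group are among the first interpretable results in SAP section 2.

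**The concern.** An outlier table shows whether individual patients moved far enough to matter, and whether more of them did so on active doses than on placebo. Here the one relative heart-rate criterion faces away from the one heart-rate direction that the nonclinical data name. The QTc signal in the same protocol section does have an upward row, so the omission is specific to heart rate.

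At stake is the reading of a descriptive safety output. If heart rate rose in many patients at the higher doses, the heart-rate rows of this table could stay empty or nearly so. A reader relying on the table alone might take that as reassurance.

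**Working it through.** The documents give no power, threshold rationale or expected frequency for this table, so there is no figure of the plan's own to reproduce.

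**Inputs from the documents.** Fall criterion 25% and high-rate criterion 130 bpm (SAP 8.2). Pulse allowed at entry 40-90 bpm (Protocol 4.1, criterion 11). Pulse range used for flagging vital signs 40-90 bpm (SAP 8.2). Applying the pulse entry range to baseline ECG heart rate is an assumption.

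**Step 1: can the 130 bpm row catch a 25% rise?** Value after a 25% rise = 1.25 × baseline. Rise needed to reach 130 bpm = 130/baseline − 1.

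| Baseline (bpm) | After a 25% fall (counted) | After a 25% rise | Counted? | Rise needed to reach 130 bpm |
|---|---|---|---|---|
| 40 | 30.0 | 50.0 | no | 225% |
| 60 | 45.0 | 75.0 | no | 117% |
| 70 | 52.5 | 87.5 | no | 86% |
| 90 | 67.5 | 112.5 | no | 44% |

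A 25% rise reaches 130 bpm only from a baseline of 130/1.25 = 104 bpm, which lies outside the entry range.

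**Step 2: does the pulse flag cover it?** A 25% rise exceeds 90 bpm only from baselines above 90/1.25 = 72 bpm. Smaller baselines give no flag, and the flag belongs to a listing, not to a count by arm.

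**Step 3: what would a symmetric row add? (illustration on assumed values)** The documents give no heart-rate variances. Assume mean 70 bpm, between-patient SD 9, visit-to-visit SD v of 4 to 8, and replicate SD r of 2 to 5, with triplicates averaged at both times. Write s² = v² + r²/3, which runs from 16 + 1.33 = 17.33 to 64 + 8.33 = 72.33.

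The new row counts a patient when post-dose − 1.25 × baseline ≥ 0. That quantity has

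- mean 70 + Δ − 87.5, where Δ is the true rise in bpm;
- SD = √[(0.25 × 9)² + s²(1 + 1.25²)], which is 7.03 to 13.80 bpm.

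At one visit:

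- No drug effect (Δ = 0, mean −17.5): Φ(−17.5/7.03) = 0.6% to Φ(−17.5/13.80) = 10%. These are chance counts.
- A true rise of 15 bpm in every patient (mean −2.5): Φ(−2.5/7.03) = 36% to Φ(−2.5/13.80) = 43%.
- The existing row under the same 15 bpm rise: the post-dose value has mean 85 and SD √(81 + s²) = 9.92 to 12.38, so the chance of exceeding 130 bpm is at most Φ(−45/12.38), about 0.01%.

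Under these assumptions the present table would record almost nothing for a rise that a symmetric row would count in more than a third of patients.

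**The case against.** The strongest reply is that the plan looks at heart-rate rises in several other places, some aimed directly at this mechanism. SAP 8.2 plots post-dose change in blood pressure and heart rate by treatment on Day 1 and Day 30, near the time of Cmax, and relates those changes to Cmax. It summarizes vital signs by treatment and visit, including upper quartile and maximum, and flags pulse outside 40-90 bpm. SAP section 2 adds mean heart-rate profiles and individual vital-sign plots, and the second interim analysis shows mean change in vital signs. A shift across a whole arm is best seen in such outputs. The signal is also modest: the protocol classes it as of undetermined relevance and not seen clinically so far, and section 3.6.2 reports no clinically relevant change in blood pressure or supine pulse in healthy volunteers.

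Most of this stands, and it limits the point. A reader might infer that the cardiac check as a whole faces the wrong way. The documents do not support that, given these displays and the upward QRS and QTcF rows. What the reply leaves open is that none of these outputs is stated to count patients with a relative rise by arm, whereas relative falls are counted that way.

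A second tempting inference is that change from baseline is taken against a single tracing. The protocol says "All ECGs are done as 12-lead triplicate ECGs", and SAP 8.1 says "Baseline for all variables, is defined to be the last measurement prior to the start of study drug administration". The SAP sentence fixes the time point and is silent on replicates; the triplicate taken at that time point can equally be the measurement meant. A single-tracing baseline is therefore not established, and no noise penalty can be attributed to it. How the three tracings are combined is simply a detail not given here.

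**Conclusion.** The point holds as a small gap in one descriptive safety table. The heart-rate rows count falls of 25% or more and miss every 25% rise from a baseline of 40 to 90 bpm. That arithmetic rests only on the documents' thresholds and on carrying the pulse entry range over to ECG heart rate. The 36-43% against about 0.01% contrast is an illustration on assumed variances and an assumed 15 bpm rise; it is not a forecast for this drug.

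The consequence is confined to patient-level counts by arm. No hypothesis test, estimate, sample size or stopping rule depends on the table. The change is a worthwhile improvement, not a necessary correction.

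**What to change.** Add a row to the ECG list in SAP 8.2 for a heart-rate increase from baseline of 25% or more, mirroring the decrease row and using the same analysis sets and visits. No new data are needed.

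The cost is one extra line per table and some counts from visit-to-visit variation alone (0.6% to 10% of patients per visit under the assumed variances above). The row should therefore be read against placebo and not taken at face value within an arm.

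Optionally, one sentence in SAP 8.1 or 8.2 could say how the three ECG tracings are combined at baseline and at later time points. That is clarification only, and the new row does not depend on it.
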